## 8.6. Efficacy analysis

### 8.6.1. Analysis of the primary efficacy endpoint

#### 8.6.1.1. Primary analysis

The primary analysis is the estimation of the success rate after 18 months of follow-up with acoziborole (cf. [Section 6.1](#)). The primary analysis will be performed on Stage 2 patients included in the mITT set.

An estimate of the success rate at 18 months will be provided. The 95% Jeffreys confidence interval of the estimate will be provided. The Jeffreys confidence interval has a coverage probability that does not exceed 95% by too much and is equal tailed, i.e. the probabilities of the interval lying above or below the upper and lower bounds are both close to 2.5%, which is important when the lower bound of the 95% confidence interval is more meaningful from a clinical standpoint than the upper bound.

#### 8.6.1.2. Sensitivity analyses

##### Sensitivity analysis #1

The analysis described above (cf. primary analysis) will be repeated on Stage 2 patients included in the PPS.

**Sensitivity analysis #2**

The analysis described above (cf. primary analysis) will be repeated on Stage 2 patients included in the Evaluable patients set.

**Sensitivity analysis #3**

The analysis described above (cf. primary analysis) will be repeated on Stage 2 patients included in the Treated set.

**Sensitivity analysis #4**

The analysis described above (cf. primary analysis) will be performed on Stage 2 patients included in the mITT with the “fair case” method (see [Section 7.6.1](#)).

**Sensitivity analysis #5**

The analysis described above (cf. primary analysis) will be performed on Stage 2 patients included in the mITT with the “best case” method (see [Section 7.6.1](#)).

**Sensitivity analysis #6**

The analysis described above (cf. primary analysis) will be performed on Stage 2 patients included in the mITT with the “observed case” method (see [Section 7.6.1](#)).

**8.6.1.3. Success Rate for the yardsticks**

As per protocol, Section 9.6.1: “The current standard of care for stage 2 patients is NECT, and the success rate with NECT will be used as a yardstick”.

“The success rates will be provided study-by-study along with the 95% Jeffreys confidence interval. Studies presented in the following table will be taken into account as well as the overall success rate excluding Nect-field. The NECTField study will not be used because it did not include the same population and the large number of missing lumbar punctures could drastically reduce the success rate, particularly at 12 and 18 months (cf. protocol, ref. 20). All of the results will be presented together in graphic format using a Forest plot”.

**Table 4: Efficacy of NECT**

| Study                         | Success rate at 18 M
for NECT ITT and 95%
Jeffreys CI        | Comments   |
|-------------------------------|--|--|
| Mesu (2017)
Fexi 004 study | S.R. = 124 / 130 = 95.4%
95% CI = [90.7% - 98.1%]               | Pivotal Fexinidazole study.
mITT: S.R.= 124 / 127 = 97.6% (RZD trial).
95% Jeffreys CI = [93.8% - 99.3%]
Reason : 3 patients fleeing the region due to armed conflict |
| Priotto (2006)                | S.R. = 16 / 17 = 94.1%
95% CI = [75.6% - 99.4%]                 | RZD trial  |
| Checchi (2007)                | S.R. = 29 / 31 = 93.5%
95% CI = [80.9% - 98.6%]                 |  |
| Priotto (2009)                | S.R. = 135 / 143 = 94.4%
95% CI = [89.7% - 97.3%]               | S.R. = 138 / 143 = 96.5%
95% Jeffreys CI = [92.5% - 98.7%]
Note: exclusion of 3 deaths not related to treatment (RZD trial)  |
| Kansiime (2018)               | S.R. = 50 / 55 = 90.9%
95% CI = [81.2% - 96.4%]                 | RZD trial  |
| Total                  | S.R. = 354 / 376 = 94.1%
95% CI = [91.4% - 96.2%] | Based on randomized studies only.  |

| Study      | Success rate at 18 M
for NECT ITT and 95%
Jeffreys CI | Comments   |
|------------|---|--|
| NECT field | S.R. = 582 / 613 = 94.9%
95% CI = [93.0% - 96.5%]        | Evaluations are not always done at M18 (one arm field study with loose monitoring). 49 lost to follow-up at M18 were not necessarily counted as failure. |

Note: percentages and their 95% Jeffrey confidence interval of success rate at 18 months will be used as they are in Table 4 (i.e. no further calculation will be performed) in the forest plot.

Note: results from Priotto 2007 [1] will not be displayed in the forest plot as it is actually a sub-cohort of patients from Priotto 2009.

Note: it could be difficult to get all individual historical data of all available studies using NECT. In other words, it will be difficult to use exactly the same criteria for determining the status of each patient treated with NECT. The figures presented in Table 4 and especially the overall estimate will be used as a yardstick even if they are more liberal (except for the Mesu's study) than what could be obtained from the strict application of algorithm. As an example, in Priotto's study (2009) 129 patients completed the M18 visit and were proven cured (i.e. WBC in CSF < 20). This represents a success rate of 88.8%. 138 patients out of 143 were considered as cured by the authors leading to a success rate of 96.5%. All deaths regardless the cause (5), relapses (2) and absence of any post-treatment assessment (1) were considered as failure in Table 4 leading to a failure rate of 5.6% (S.R. = 94.4%). Lost to follow-up due to moved out (2 patients moved out) and absence of assessment (probably lumbar puncture) at M18 (4 patients) are not counted as failures in Table 4 and this sort of decision is a potential source of bias (overestimation of success rate of NECT compared to the strict application of the algorithm). Because the retained result in Table 4 is rather in favour of NECT, the possible bias is in disfavour of acoziborole when the yardstick (NECT) is compared to acoziborole.

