## Success Rate for the Yardstick

The current standard of care for late-stage patients is NECT, and the success rate with NECT will be used as a yardstick.

The success rates will be provided study-by-study along with the 95% Jeffreys confidence interval. Three studies will be taken into account: the study by Priotto et al. (18) involving 143 patients exposed to NECT; the WHO-TDR study (13) involving 55 patients exposed to NECT; and the DNDiHATFEX004 study involving approximately 130 patients exposed to NECT. Data from the NECT-Field study will not be used because it did not include the same population and the large number of missing lumbar punctures could drastically reduce the success rate, particularly at 12 months (20). All of the results will be represented together in graphic format using a Forest plot.

The method described in Section 2.2.1 Primary Endpoint - Efficacy concerning analysis of the primary endpoint will not be used directly on the historical data as no raw data are available. However, all deaths, regardless of the cause, will be considered as failures. For estimates in the literature, the classification method described in the publications will be applied to the data on acoziborole to ensure that successes are the same in nature. Differences in the definitions will be explicitly identified. In all cases, the mITT set of patients will be used. In all cases, the Jeffreys confidence interval will be used.

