## 5. ANALYSIS SETS AND SUBGROUPS

The analysis sets are defined below:

- **Set of screened HAT positive patients:** All HAT positive patients who signed the informed consent. To be noted that after the 1st DSMB meeting, recruitment of stage 1 and intermediate stage HAT patients was authorized. That will trigger a modification of the initial screened set.
- **Treated set:** all patients who received at least one tablet of acoziborole.
- **Modified Intention-To-Treat (mITT):** All patients who received at least one tablet of acoziborole, excluding patients (\*) who fled the region due to armed conflict or natural disaster or due to force majeure (\*\*) and for whom no failure was detected early (parasite, needs for rescue medication, death or more than 50 WBC/µL in CSF at M6) and no data are available at M12 and M18 due to armed conflict, natural disaster or force majeure affecting the site.
- **Evaluable patients:** Modified Intent-to-treat patients (mITT) and excluding:
  - Patients lost to follow-up at 18 months (for primary efficacy endpoint and secondary efficacy outcome at 18 month), patients lost to follow-up at 12 months (for secondary efficacy outcome at 12 month), patients lost to follow-up at 6 months (for secondary efficacy outcome at 6 month), except those who were a failure before being lost to follow-up (cf. [Section 7.7](#) for programming rules).
  - Patients with no post-treatment lumbar puncture (i.e. patients who refused all lumbar puncture after treatment and who were not a failure)
  - Patients who died for reasons clearly unrelated to efficacy or safety or disease evolution (\*\*).
  - Early consent withdrawal (before M6, i.e. no planned visit attended after 3-month visit).
- **Per Protocol Set (PPS):** Modified Intent-to-treat patients (mITT) with no major protocol deviations (\*\*\*). Major deviations will be described by patient, and exclusion will be decided during the data review (cf. [Section 8.2](#)).

Notes:

(\*) These patients will be included in the Treated set population as failures.

(\*\*) This will be reviewed during data review meeting (e.g. review of comments and reasons of early discontinuation in end-of-study form).

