**14.2.1.3 Forest plot of success rate at 18 months for the yardstick - Stage 2 patients (mITT)**

**9.1.3. List of outputs for ICH Section 14.2.2 (Secondary efficacy endpoints)**

**14.2.2 Secondary efficacy endpoints**

**14.2.2.1 Outcome at 12 months in stage 2 patients**

**14.2.2.1.1 Primary analyses**

14.2.2.1.1.1: Success rate at 12 months – Stage 2 patients (mITT)

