### 9.2.15. Forest plot of success rate for the yardsticks

| Study                                     | Success rate (%) at M18 | Jeffrey 95% CL |
|---|-------------------------|----------------|
| 1. Mesu 2017 (Fex004) (success=124 / 130) | 95.4                    | 90.7-98.1      |
| 2. Priotto 2006 (success=16 / 17)         | 94.1                    | 75.6-99.4      |
| 3. Checchi 2007 (success=29 / 31)         | 93.5                    | 80.9-98.6      |
| 4. Priotto 2009 (success=135 / 143)       | 94.4                    | 89.7-97.3      |
| 5. Kansiime 2018 (success=50 / 55)        | 90.9                    | 81.2-96.4      |
| 6. Total (success=354 / 376)              | 94.1                    | 91.4-96.2      |
| 7. NECT field (success=582 / 613)         | 94.9                    | 93.0-96.5      |
| 8. DNDI-OXA-02-HAT (success=xxx / xxx)    | xx.x                    | xx.x-xx.x      |

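### The yardstick forest plot sets acoziborole on mITT against an ITT figure for the pivotal fexinidazole trial's NECT arm, so patients who fled are treated in opposite ways on that row

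*SAP*

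**What the plan says.** Protocol 9.6.1, under the yardstick heading, says: "In all cases, the mITT set of patients will be used".

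SAP 9.1.2 lists one yardstick plot, output 14.2.1.3: "Forest plot of success rate at 18 months for the yardstick - Stage 2 patients (mITT)". Its template (SAP 9.2.15) has a single row for this trial, "DNDI-OXA-02-HAT (success=xxx / xxx)", and a fixed row for the pivotal fexinidazole trial's NECT arm, "Fex004) (success=124 / 130)".

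That fixed row comes from SAP Table 4 (8.6.1.3), whose rate column is headed ITT and reads "S.R. = 124 / 130 = 95.4" per cent. The comments cell of the same row gives the mITT result, 124/127 = 97.6%, and explains the difference: "3 patients fleeing the region due to armed conflict". A note under the table says the rates and intervals "will be used as they are in Table 4 (i.e. no further calculation will be performed) in the forest plot".

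For acoziborole, SAP section 5 defines mITT so that a patient who fled is removed if no early failure was detected and "no data are available at M12 and M18 due to armed conflict, natural disaster or force majeure affecting the site". The same patients return as failures in the Treated set, which is used in sensitivity analysis #3 (SAP 8.6.1.2, output 14.2.1.2.3).

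SAP section 11 declares protocol 9.6.1 modified and reprints the ITT-headed table. It does not mention the protocol's mITT rule.

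**The concern.** On this row the two treatments follow opposite rules for the same event. A NECT patient who fled is a failure; an acoziborole patient who fled and meets the mITT exclusion leaves the denominator. The title of the output tells the reader that everything shown is mITT.

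The row matters because both documents say there is no objective criterion for success: the acoziborole rate and its lower confidence bound are to be interpreted against the literature and historical data. This trial is the recent comparator singled out in the regulatory advice quoted in SAP 8.6.1.4, which cites its 97.6% cure rate. That number does not appear on the plot.

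The note in SAP 8.6.1.3 excepts this trial when it calls the NECT figures liberal, but then concludes in general terms that any bias works against acoziborole. For this row, once any acoziborole patient is excluded as fled, the bias runs the other way.

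**Working it through.** **Method.** Equal-tailed 95% Jeffreys interval for x successes in n: the 2.5% and 97.5% quantiles of Beta(x + 0.5, n − x + 0.5).

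**1. Reproduce the plan's figures (SAP Table 4).**
- 124/130 = 95.38% [90.74, 98.05]; printed 95.4% [90.7, 98.1].
- 124/127 = 97.64% [93.83, 99.33]; printed 97.6% [93.8, 99.3].
- Total: 124 + 16 + 29 + 135 + 50 = 354 and 130 + 17 + 31 + 143 + 55 = 376, giving 94.15% [91.43, 96.19]; printed 94.1% [91.4, 96.2].

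The numerator is 124 in both versions of the pivotal-trial row, and 130 − 127 = 3, so the three who fled are failures in the plotted figure.

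**2. Effect on the NECT side.**
- Pivotal-trial row: estimate 97.64 − 95.38 ≈ 2.3 points higher on mITT; lower bound 93.83 − 90.74 ≈ 3.1 points higher.
- Total with only those three removed: 354/373 = 94.91% [92.32, 96.80], about 0.8 points higher.

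**3. Effect on the acoziborole side.** The documents do not give the number excluded as fled, so call it k. It is an assumption, shown from 0 to 7, where 7 is the replacement provision in protocol 9.1. Assume 155 patients in mITT and 155 + k in the Treated set, with the k counted as failures. The protocol's two precision scenarios reproduce with whole numbers: 138/155 = 89.03% [83.40, 93.23] (printed 83.4 to 93.2) and 146/155 = 94.19% [89.67, 97.09] (printed 89.7 to 97.1).

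| k | Treated set, 94% scenario | Fall from mITT, 94% scenario | Fall from mITT, 89% scenario |
|---|---|---|---|
| 0 | 146/155 = 94.2% [89.7, 97.1] | 0 | 0 |
| 1 | 146/156 = 93.6% [88.9, 96.7] | 0.6 | 0.6 |
| 3 | 146/158 = 92.4% [87.5, 95.8] | 1.8 | 1.7 |
| 7 | 146/162 = 90.1% [84.8, 94.0] | 4.1 | 3.8 |

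**4. What the reader would see.** Acoziborole minus the pivotal-trial row, 94% scenario, k = 3:
- as planned, mITT against 124/130: 94.2 − 95.4 = −1.2 points;
- both on mITT, against 124/127: 94.2 − 97.6 = −3.4 points;
- both with the fled as failures, Treated set against 124/130: 92.4 − 95.4 = −3.0 points.

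Either consistent pairing gives a gap more than twice the one plotted. At k = 0 the Treated set equals mITT, and the Treated-set comparison with 124/130 is −1.2, the same as plotted.

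**5. Related arithmetic in the SAP 8.6.1.3 note.** In the 143-patient trial of 2009, 8 failures, 2 who moved out and 4 without an 18-month assessment leave 143 − 8 − 2 − 4 = 129. The note calls this 88.8%, but 129/143 = 90.2%; 88.8% is 127/143.

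**The case against.** The protocol sentence can be read as fixing only the acoziborole set. It follows a statement about applying published classifications to acoziborole data; protocol mITT is defined by receipt of acoziborole; and the same section describes the historical trials by patients exposed, including about 130 for this one. Section 11 shows the ITT heading openly. The 97.6% appears in Table 4 and in the quoted advice, the Treated-set result has its own output, and the number excluded from mITT can be recovered from the analysis-set tables and listings. The mismatch disappears if nobody is excluded as fled. No hypothesis test depends on the plot.

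Much of this limits the size of the problem without removing it. The narrow reading of the protocol is weak: the sentence sits under the yardstick heading next to a parallel one requiring Jeffreys intervals in all cases, which plainly covers the historical rates. The mismatch on the plot exists on either reading. Section 11 reprints the table without withdrawing or justifying the mITT rule.

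Three points stand:

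- The effect is conditional on k, and k = 7 is a provision, not a forecast.
- The SAP puts most weight on the Total, where no net bias is shown. Six patients in the 2009 trial are not counted as failures. Counting the two who moved out gives 352/373 = 94.4% and counting all six gives 348/373 = 93.3%, on either side of the printed 94.1%.
- The pivotal trial's own mITT definition is not given and may differ from the SAP's, so 124/127 is the closest available match, not a verified one.

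**Conclusion.** The concern holds for the pivotal-trial row and should be fixed. An output labelled mITT carries an ITT figure that is 2.3 points lower than the mITT figure printed beside it in Table 4, with a lower bound 3.1 points lower, and the protocol's mITT rule is departed from without being acknowledged. Whether this distorts the comparison depends on whether any acoziborole patient is excluded as fled. If at least one is, the row favours acoziborole; under the stated assumptions the fall from mITT to the Treated set is 0.6 points for one such patient and about 4 points for seven. If none is, 124/130 is consistent with the acoziborole result, and only the labelling and the undeclared departure remain. No net bias is claimed for the Total.

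**What to change.** - In template 9.2.15 and the plot, show 124/127 beside acoziborole mITT, and 124/130 beside the acoziborole Treated set. Label the analysis set on every row.
- State on the plot the number of acoziborole patients excluded as fled. If it is zero, say that the two acoziborole rows coincide.
- Keep 354/376 as the ITT Total. If 354/373 is also shown, label it as a mixture of one mITT row and four ITT-headed rows.
- Footnote that the other rows handle lost patients differently and that the pivotal trial's mITT definition may not match the SAP's.
- In section 11, record and justify the departure from the protocol's mITT rule. Also record that the protocol's plan to apply the published classifications to the acoziborole data has no corresponding SAP analysis.
- In the SAP 8.6.1.3 note, say that the closing sentence on direction of bias does not apply to the pivotal trial, and reconcile 129/143 with the printed 88.8%.

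The cost is SAP text, one template and one plot. The 124/127 rate and interval are already in Table 4 and the Treated-set analysis is already planned.

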### Success Rate for the Yardsticks:

Section 9.6.1 of the Protocol version 4.0 has been modified in this SAP version as follows. Revised text is written in bold and red.

**“Success Rate for the Yardstick:** The current standard of care for stage 2 patients is NECT, and the success rate with NECT will be used as a yardstick. The success rates will be provided study-by-study along with the 95% Jeffreys confidence interval. **Three studies will be taken into account: the study by Priotto et al. (cf. protocol, ref. 17) involving 143 patients exposed to NECT; the WHO-TDR study involving 55 patients exposed to NECT; and the DNDiHATFEX004 study involving approximately 130 patients exposed to NECT. Data from Studies presented in the following table will be taken into account as well as the overall success rate excluding Nect-field.** The NECTField study will not be used because it did not include the same population and the large number of missing lumbar punctures could drastically reduce the success rate, particularly at 12 **and 18** months (cf. protocol, ref. 20). All of the results will be presented together in graphic format using a Forest plot (except for NECTfield).

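### The SAP drops, undeclared, the protocol's step of applying the published NECT success rules to the acoziborole data, leaving forest-plot rows mismatched in both directions

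*SAP*

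**What the plan says.** Protocol 9.6.1 (Success Rate for the Yardstick) accepts that raw NECT data are unavailable, so the trial's own endpoint rule cannot be run on the historical patients. It therefore converts in the other direction: "the classification method described in the publications will be applied to the data on acoziborole to ensure that successes are the same in nature". It adds "Differences in the definitions will be explicitly identified" and "In all cases, the mITT set of patients will be used". It also requires every death, whatever its cause, to count as a failure.

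SAP 8.6.1.3 presents itself as following that section but stops at the forest plot, before the paragraph on classification. The Table 4 figures enter the plot unchanged: "i.e. no further calculation will be performed) in the forest plot". The SAP says they "will be used as a yardstick even if they are more liberal" than its algorithm would give, with the pivotal fexinidazole trial as the stated exception. It explains the differences for one study only, the 2009 randomised NECT trial, as an example: there, patients who moved away or had no month-18 assessment "are not counted as failures in Table 4 and this sort of decision is a potential source of bias".

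Output 14.2.1.3 is a single plot on mITT, and template 9.2.15 has one acoziborole row. SAP Section 11 announces that "Section 9.6.1 of the Protocol version 4.0 has been modified in this SAP version as follows" and gives a new study list. It does not mention the classification step.

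**The concern.** Both documents state that there are no objective rules for success. The observed rate and its lower confidence bound are to be interpreted against the literature and historical data, so the yardstick plot carries much of the interpretation. If its rows score the same kind of patient differently, the gap between them mixes drug effect with outcome definition.

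The SAP explains why it cannot apply its algorithm to NECT patients: individual data would be needed. The conversion the protocol promised needs only this trial's data and the published rules. A reader who relies on Section 11 for departures from the protocol would not learn that this step had gone.

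**Working it through.** **Reproducing Table 4.** The equal-tailed Jeffreys interval takes the 2.5% and 97.5% quantiles of Beta(x + 0.5, n − x + 0.5). For the 2009 trial the SAP prints "S.R. = 135 / 143 = 94.4"%; the calculation gives 94.4% [89.7–97.3], as printed. The pooled 354/376 gives 94.1% [91.4–96.2], also as printed. The other rows reproduce to rounding.

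**The 2009 row.** Counts from SAP 8.6.1.3:
- Table 4 failures: 5 deaths + 2 relapses + 1 with no post-treatment assessment = 8, so 143 − 8 = 135 successes.
- Kept as non-failures: 2 who moved away and 4 with no month-18 assessment.

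Under the acoziborole algorithm (SAP 10.1, stage 2), loss to follow-up at month 18 is failure at step 4, so the two who moved become failures. The four are undetermined. Steps 7–8 accept a later reliable CSF count. Step 11 gives success without a month-18 puncture if earlier counts are acceptable and there are no symptoms suggesting relapse.

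| Rule applied to the same 143 patients | Successes | Rate [95% Jeffreys CI] |
|---|---|---|
| Authors' classification | 138 | 96.5% [92.5–98.7] |
| Table 4 (all deaths failures) | 135 | 94.4% [89.7–97.3] |
| Only the 2 who moved become failures | 133 | 93.0% [88.0–96.4] |
| All 6 become failures | 129 | 90.2% [84.5–94.3] |

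Shift from Table 4: 2/143 = 1.4 points to 6/143 = 4.2 points.

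**Pooled yardstick, changing that study only.** 352/376 = 93.6% and 348/376 = 92.6%, a fall of 2/376 = 0.5 to 6/376 = 1.6 points.

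**The fexinidazole-trial row.** Plotted: 124/130 = 95.4% (ITT). On mITT, without the 3 patients who fled armed conflict: 124/127 = 97.6%, which is 2.2 points higher. With that change alone the pooled rate would be 354/(376 − 3) = 354/373 = 94.9%, about 0.8 points higher. Acoziborole is plotted on mITT, so this row flatters acoziborole.

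**Illustration for the acoziborole row.** The documents contain no results. Assume 155 patients, 146 successes under a published-type rule, and 0 to 6 patients whose status depends on the rule. The rate runs from 94.2% [89.7–97.1] through 92.9% [88.1–96.2] with two such patients to 90.3% (140/155) [84.9–94.2] with six. The lower bound then moves by up to just under 5 points.

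**A slip in the same paragraph.** The SAP prints 88.8% for the 129 proven cured. In fact 129/143 = 90.2%; 88.8% is 127/143. The count agrees with the SAP's own tally (143 − 8 − 6 = 129), so the percentage is what needs correcting.

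**The case against.** The best reply is that the SAP is open about the problem. It gives the patient counts, calls the choice a possible source of bias and says the direction is against acoziborole. For the 2009 trial that partly meets the promise to identify definition differences. The error there is conservative for the drug, the primary estimate is untouched, and no decision rule depends on the plot. All of that stands. But disclosing a bias does not replace a pre-specified remedy that can be carried out, and what Section 11 leaves unsaid is that the remedy was removed.

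A second reply is that other analyses bound the effect. The evaluable set drops patients lost to follow-up who had not already failed. The fair-case method resamples them, the best-case method counts them as successes, and the observed-case method treats missing month-18 data as missing. This softens the problem. None of these is on the plot, however, and none reproduces a published rule. Best case also turns refusal of all post-treatment punctures into success, whereas Table 4 counts the absence of any post-treatment assessment as failure.

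Nor is the plot the only planned NECT comparison. SAP 8.6.1.4 describes adjusted, stratified and propensity-score analyses, but they depend on databases that may not be recovered.

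Three stronger readings are tempting but unsupported:
- *The whole NECT yardstick is lenient.* The SAP exempts the fexinidazole trial, 130 of the 376 pooled patients, and that row is mismatched in the opposite direction.
- *Definition alone costs 4.2 points.* That is the upper end, reached only if the algorithm would fail all four unassessed patients.
- *The shift exceeds the lower arm of the pooled interval* (94.1 − 91.4 = 2.7 points). That sets a one-study shift against a pooled interval. Like for like, the pooled shift is at most 1.6 points, and 4.2 is below the 2009 trial's own lower arm of 94.4 − 89.7 = 4.7 points.

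**Conclusion.** The point holds. A protocol commitment on the contextual comparison is not implemented in the SAP's methods or outputs, and its removal is not declared. The rows differ in outcome rule and in analysis set, and not all in one direction, so the SAP's statement that the bias disfavours acoziborole cannot be extended to every row.

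Measured by applying the acoziborole algorithm to the 2009 trial, the rule mismatch is about 1.4 to 4.2 points on that row and 0.5 to 1.6 points on the pooled rate. The set mismatch on the fexinidazole-trial row is 2.2 points the other way.

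These sizes rest on the SAP's patient counts and on the two who moved having no later information. Where the truth lies within the range depends on the four unassessed patients, about whom the documents say nothing more. The other three pooled rows (17, 31 and 55 patients) cannot be sized because no breakdown is given. The effect on the acoziborole row itself is unknown until there are data. This should be fixed for interpretation; it does not threaten the primary estimate.

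**What to change.** 1. In SAP 8.6.1.3 and output 14.2.1.3, add a second acoziborole row labelled *published classification*, marked as contextual, beside the algorithm-based row. Derive it by the rule behind the 2009 row as SAP 8.6.1.3 states it. All deaths, relapses and absence of any post-treatment assessment are failures; having moved away or lacking a month-18 assessment is not. Confirm any further condition from the publication, since the documents do not give the full rule.
2. Do the same for each other publication that states its rule, and add a short table of definition differences by study.
3. Plot the fexinidazole-trial NECT row on mITT, or show ITT and mITT together.
4. If any part is not done, declare and justify it in Section 11.
5. Correct 88.8% to 90.2% for 129/143.

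The cost is one derived variable and one plot row per published rule, plus a small table. No new data are collected and the primary estimate stays as it is. The downside is that the extra row will be more lenient to acoziborole, so its label must make clear that it is context and not the trial's result.
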